Infants with intestinal failure require chronic administration of parenteral nutrition (TPN). The population under one year of age on TPN is at greatest risk for parenteral nutrition associated cholestasis (PNAC), but, even among older individuals on TPN, the emergence of cholestasis carries a bad prognosis. A number of factors play a role in PNAC. These include endotoxemia, prolonged fasting, immaturity of bile secretory mechanisms among infants, intravenous infusion of high glucose concentrations, intravenous infusion of high protein loads, and intravenous infusions of soy based lipid emulsions. Human data reveal that TPN administered to infants for over three weeks is associated with PNAC. Further analysis reveals that cholestasis is closely associated with the administration of soy-based lipids which contain potentially hepatotoxic phytosterols. Thus lipid reduction strategies have been employed for reversal of PNAC. They sometimes work, but put infants at risk for essential fatty acid deficiency. An alternative strategy of providing lipid in the form of Omegaven®, a fish oil-derived emulsion, is extremely promising, and has been used successfully with virtually no complications in an uncontrolled trial at Boston Children's Hospital. Ongoing controlled studies of Omegaven® are underway at Boston Children's Hospital, and several other institutions have published small case series or case reports suggesting that Omegaven® is effective and safe. It is not FDA approved because none of the ongoing placebo controlled trials have been completed yet in the United States, but, because of its anti-inflammatory properties, it is approved in several European countries for use in adults with inflammatory conditions. Every year, we observe several children in our own practice who have no hope of coming off TPN for several months and who have progressive cholestasis. Our own unpublished data suggest that once PNAC has been established in the absence of endotoxemia, it is usually reversible. However, this may not be true if less than approximately 70% of daily calories are derived enterally. We also have published data in abstract form suggesting that a high conjugated bilirubin to gamma GT ratio is a poor prognostic sign. This study provides Omegaven® for compassionate release to those infants within our practice who have developed progressive cholestasis despite reduction in parenteral lipid below one gram per kilogram

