body weight per day, and who are unlikely to tolerate substantial enteral nutrition until several months following their small intestinal insult.

II. Purpose of Study

The specific aim of this study is to ascertain whether PNAC can be reversed if a fish oil-based intravenous lipid product (Omegaven®) at a dose of up to 1 g/kg body weight/day is substituted for a soy-based intravenous lipid product (Liposyn® or Intralipid®) as part of the daily TPN of infants and children with intestinal failure and PNAC. Secondary aims will be to confirm the safety of Omegaven®.

III. Background

In North America, infants and children who require parenteral nutrition (TPN) customarily receive solutions whose caloric distribution is balanced between glucose, protein, and fat to provide approximately 60-70 % of calories via glucose, 10-15 % of calories via protein, and 20-30% of calories via lipid.(1) Commercial lipid solutions utilized in North America are customarily soy-based, and contain high quantities of phytosterols including sitosterol and stigmasterol. Animal data suggest that high quantities of stigmasterol inhibit fxr, a nuclear receptor in the hepatocyte that helps to regulate bile acid homeostasis by controlling expression of bile acid export pumps. (2) Thus, exposure to a high quantity of stigmasterol is potentially hepatotoxic to individuals who have a propensity for cholestasis due to a poorly developed bile secretory process.

It is known that infants and children with underlying intestinal failure are at extraordinarily high risk for cholestasis. (3) The cholestatic process is reversible in approximately ¼ of infants with parenteral nutrition associated cholestasis (PNAC), even when soy-based lipid emulsions are given parenterally, if those infants can experience small intestinal adaptation and ultimately tolerate and assimilate the majority of their calories via enteral nutrition. Unfortunately, if adaptation does not occur rapidly enough, PNAC may progress to endstage liver disease resulting in death or necessitating combined liver/small intestinal transplantation.

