A popular strategy for minimizing the toxicity of lipid emulsions is to reduce the amount of lipid in parenteral nutrition to between 0.5 g/kg body weight/day and 1g/kg body weight/day. (4) Preliminary results suggest that this strategy is beneficial for some infants, but that it is not universally effective. One potential reason for lack of effectiveness among some cholestatic infants is that endotoxemia is commonplace in children with intestinal failure receiving TPN, and that stigmasterol potentiates the cholestatic effect of endotoxin upon the liver. Therefore, when the infant with a cholestatic propensity is exposed to endotoxin and even modest quantities of stigmasterol, cholestasis could progress.

An alternative liver-protective strategy for children on TPN has been to provide all of the patients' parenteral lipid in the form of a fish-oil based product called Omegaven®. (5) This product has been used for over 10 years as an adjunct to conventional fat emulsions.

According to current data, an increase in the proportion of omega-3 fatty acids is thought to optimize nutrition in general, but in particular benefit patients whose underlying disease might benefit from an increase in omega-3 fatty acids. An adequate intake of omega-3 fatty acids results in anti-inflammatory and immunomodulatory effects that are protective against inflammatory tissue damage and capillary permeability. In addition, adults on Omegaven® seem to display improved immunological resistance. Omegaven® may also reduce the risk of thrombosis and increase microvascular perfusion due to its anti-aggregatory and vasodilatory effects.

In Europe and Asia, parenteral omega-3 fatty acids have been used in the following adult patient populations:

1. post traumatic and post surgical patients
2. patients experiencing early stages of sepsis/SIRS
3. patients at risk of hyperinflammatory processes
4. patients with inflammatory bowel disease (Crohn's disease, ulcerative colitis)
5. patients with inflammatory skin diseases (psoriasis, atopic eczema)

The dosing used in these patients was 0.1 (1ml) to a maximum of 0.2 g (2ml) /kg body weight. The infusion rate used did not exceed 0.5ml/kg/body weight/hour. Since it was intended to be infused in combination with conventional fat emulsions, the total fat intake was limited to 10-20% as fish oil. The duration of administration did not exceed 4 weeks.

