5. Lack of appetite, nausea, vomiting
6. Dyspnea
7. Headache, pain in the chest, bone pain
8. Priapism
9. Increase/decrease blood pressure
10. Anaphylactic reactions/erythema

Risks for blood draw:

- Occurrence of discomfort and/or a bruise at the site of puncture
- Less commonly, fainting
- The formation of a clot or swelling in the vein and surrounding tissue
- Bleeding from the puncture site
- On rare occasions an infection may develop at the site where the blood is collected

Potential Risks of No Treatment

Since Omegaven® will only be offered to those patients for whom no standard therapy has been safe and effective, the risks of not being treated are those allowing for the natural history of their disease and associated clinical manifestations to progress. These include fulminate liver failure and death.

VII. Overall Risk Assessment

Patients will be at some risk inherent in taking a pharmaceutical agent that has not been fully evaluated for long duration treatment. However, the availability of safety data demonstrates no life-threatening risks or toxicities to vital organs or physiologic functions. The potential benefits of Omegaven® in this patient population are mainly based on human trials and our own experience.

VIII. Risk Category

The research involves greater than minimal risk, but presents the prospect of direct benefit to the individual subjects.

IX. Methods

A. Subject Selection

No concomitant medications will prohibit enrollment.

Inclusion Criteria

1. Males and females ages one month of age to 18 years of age
2. Patients with intestinal failure on TPN
3. Patients who have a conjugated or direct bilirubin of ≥ 3 mg/dl for more than 4 weeks and in whom other causes of cholestasis have been excluded with reasonable certainty utilizing biochemical, serologic, microbiologic, and radiographic techniques. Liver biopsy is not required to rule out other disorders, but may be utilized at the clinician's discretion
4. Patients in whom reduction of IV soy-based lipid load to an **average** <1.2 g/kg body weight/day has failed to reduce the conjugated or direct bilirubin within ≥ 30 days of implementation

5. Willing to use birth control during study participation for females of child-bearing potential, as determined by investigator.
6. Signed informed consent for use of Omegaven® obtained

Exclusion Criteria

1. Any of the contraindications to use of Omegaven®

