Contact will occur by telephone unless subjects are seen in the clinic or are hospitalized. Applicable clinical records obtained at clinic visits and during hospitalizations such as H&Ps, labs, and medications can be used for research purposes.

Treatment with Investigational Drug

For the first two days of treatment, subjects will receive Omegaven® at 0.5 g/kg per day to assess tolerance and will progress to a maintenance dosage range of 0.8 to 1.2 g/kg/day over 12 hours at an infusion rate approximating 1 g/kg/12 hours (10 ml/kg/12 hours). The 12-hour infusion time will be used to minimize waste because of Centers for Disease Control and Prevention requirements that source containers of lipid emulsion be changed every 12 hours. Dosing is based on previously described dosing of fish-oil emulsions as monotherapy noted within the literature (8). Omegaven® will be infused intravenously through either a central or peripheral catheter in conjunction with other parenteral nutrition containing dextrose and amino acids. Omegaven® is isotonic. It is compatible with parenteral nutrition solutions and may be co-infused via y-site.

While hospitalized, serum triglyceride levels will be monitored weekly to insure that triglyceride concentrations do not exceed 1000 mg/dl during the infusion of fat emulsion. During hospitalization, coagulation studies will also be conducted weekly. PT and PTT will be conducted at baseline and then monthly. Other laboratory tests will be conducted to monitor for blood glucose metabolism, electrolyte and fluid balance and liver and kidney function in accordance with current institutional standards for monitoring hyperalimentation. Thromboelastography (prefer with platelet mapping) will be obtained at baseline and approximately 10 days prior to scheduled surgery to assess platelet aggregation dysfunction.

Urine pregnancy tests will be performed at baseline and monthly thereafter for females of child-bearing potential.

The patient will be observed for signs of metabolic overload and other adverse events. Adverse events will be documented by the study staff and may be used as a rationale for dosage adjustments of the study drug.

Study Drug Administration

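### The introduction limits the population to failures at below 1 g/kg/day of parenteral lipid, inclusion criterion 4 admits failures at an average below 1.2, and the registry controls carry no such condition

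*Combined protocol and SAP*

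**What the plan says.** The protocol states the level of soy-lipid reduction in three places.

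- **Introduction** (the text before Section II): Omegaven is for infants whose cholestasis has progressed "despite reduction in parenteral lipid below one gram per kilogram" of body weight per day.
- **Section III, Background:** a popular way to limit lipid toxicity is to "reduce the amount of lipid in parenteral nutrition to between 0.5 g/kg body weight/day and 1g/kg body weight/day".
- **Section IX.A, inclusion criterion 4:** reduction of soy lipid to an average "<1.2 g/kg body weight/day has failed to reduce the conjugated or direct bilirubin" within 30 or more days. No averaging period or daily maximum is given.

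Two other statements bear on how these are read. Under Potential Risks of No Treatment (Section VI), Omegaven "will only be offered to those patients for whom no standard therapy has been safe and effective". Section IX.F gives an Omegaven "maintenance dosage range of 0.8 to 1.2 g/kg/day", while Sections II and IV speak of up to 1 g/kg/day.

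For the comparison group, Sections X and XIII name historical controls from the internal registry who showed cholestasis while on Intralipid. No lipid dose, and no failed attempt at reduction, is required of them. Section XIII plans crude and adjusted hazard ratios from Cox models but names no covariates.

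**The concern.** The introduction tells the reader who the results apply to, but criterion 4 decides who is enrolled, and the two differ. A report that describes the enrolled children in the introduction's terms would misdescribe any child who entered at an average between 1.0 and 1.2 g/kg/day.

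The same variable matters for the comparison. Section III says that lipid reduction helps some infants. Treated children are selected because reduction did not lower their bilirubin, whereas the controls are not selected in that way. The control group may include children who would have improved on reduction alone, which would work against Omegaven. It may also include children on higher soy-lipid doses, which on the protocol's own account of soy-lipid toxicity would work in Omegaven's favour. The direction of any bias cannot be told from the documents.

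**Working it through.** **1. The plan's own figure.** Section XIII gives 19 patients and 19 controls for 10% against 50% resolution at 8 weeks, alpha 0.05 and 0.80 (called beta, read here as power). Taking alpha as two-sided, the arcsine formula is n = 2 × [(1.960 + 0.842) / h]², with h = 2·asin(√0.5) − 2·asin(√0.1) = 0.927. This gives 18.3, so 19 per group, as stated. The pooled normal approximation without continuity correction gives 20 per group, and power at 19 + 19 is 79.2%. Lipid dose is not an input to any of these, so for the stated rates the choice of threshold changes nothing here.

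**2. The three thresholds side by side.**

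| Place | Lipid level | Role |
|---|---|---|
| Introduction | below 1 g/kg/day | describes the population |
| Section III | 0.5 to 1 g/kg/day | describes a strategy |
| Criterion 4 | average below 1.2 g/kg/day | decides eligibility |

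The gap between criterion 4 and the introduction is 1.2 − 1.0 = 0.2 g/kg/day, or 0.2 / 1.0 = 20%. A child averaging above 1.0 and below 1.2 meets criterion 4 and neither of the other two descriptions. A child at exactly 1.0 misses the introduction's wording but is inside Section III's range.

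**3. What an average permits.** Assume a 30-day averaging period, since none is stated. Five days at 2 g/kg and 25 days at 1.0 give (10 + 25) / 30 = 1.17, which qualifies. Six such days give (12 + 24) / 30 = 1.20, which does not. The recorded average, not a nominal target, is therefore the quantity to capture.

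**4. Does the gap create the change in lipid load at the switch?** The relative cut is (entry dose − Omegaven dose) / entry dose.

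- 1.19 to 0.8: 0.39 / 1.19 = 33%
- 1.19 to 1.0: 0.19 / 1.19 = 16%
- 0.99 to 0.8: 0.19 / 0.99 = 19%
- 0.8 to 1.0: an increase of 0.2 / 0.8 = 25%

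The third case lies inside the introduction's population and still has a sizeable cut; the fourth goes the other way. Total lipid can change at entry under either threshold, because it depends on both the entry dose and the maintenance dose.

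**5. The controls.** Against criterion 4, the control definition lacks both elements: a ceiling on soy-lipid dose and a failure to respond to reduction. Neither 1.0 nor 1.2 is shown to apply to them.

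**The case against.** The strongest reply is that criterion 4 is explicit and operative, while the introduction and background are descriptive; nobody enrolling a child would be in doubt. That is right about enrolment. It does not settle how the population is to be described, and it leaves the controls untouched.

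Several stronger readings are tempting, and the documents do not support them.

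- A reader might infer that children in the gap never had a lipid reduction. They did: criterion 4 requires one, without a fall in bilirubin. It simply need not have gone as low as the introduction says.
- A reader might see a direct contradiction with the statement in Section VI about standard therapy. That section does not define standard therapy as soy lipid below 1 g/kg/day.
- A reader might take the remark in Section III that this protocol's criteria are stricter as evidence that the IRB was told something else. The remark compares this protocol with protocol 2009-1041, whose criteria are not supplied, and criterion 4 is itself part of what was submitted.
- A reader might hold that the gap is what confounds lipid type with lipid amount, and that analysing only children below 1 g/kg/day would isolate the effect of substitution. Step 4 shows otherwise: the dose can change below 1 g/kg/day too.
- A reader might want a count of affected children. The documents give no basis for one, and it could be near zero.

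It is also fair to say that the missing condition on controls would exist at either threshold. That is so, and it is why aligning the two introductory passages with criterion 4 is not enough.

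**Conclusion.** The inconsistency is real and stands in current text. The stated population stops at 1 g/kg/day, the eligibility rule runs to an average just under 1.2, and no reason for the difference is given. Its direct size is a ceiling 0.2 g/kg/day (20%) higher for an unknown number of the planned 25 children. It is a mismatch in the description of the population, not an error of calculation.

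The more consequential part is comparability. Treated children must have failed a soy-lipid reduction and controls need not have. The hazard ratio may therefore partly reflect that difference, in a direction and by an amount that cannot be determined here. This conclusion rests only on the control definition as written in Sections X and XIII; it would fall away if the registry already restricts controls in this way, which the documents do not say. Which threshold is clinically right is not judged.

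**What to change.** 1. Reconcile the introduction, Section III and criterion 4 to one soy-lipid threshold, chosen by the sponsor, with the averaging period stated. Describe the population in reports accordingly.
2. Apply the same failed-reduction condition, over the same kind of qualifying period, when selecting registry controls.
3. From TPN orders, derive each child's average soy-lipid dose over the qualifying period and, for treated children, the Omegaven maintenance dose. Report both.
4. Name the pre-entry soy-lipid dose as a covariate in the adjusted Cox model that Section XIII already plans.

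The cost is protocol wording, some added data extraction for patients and controls, and possibly a smaller pool of registry controls. Criterion 4 cannot be checked at screening without the soy-lipid dose, so for treated children the information should already be in the chart.

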The primary endpoint will be reduction in conjugated or direct bilirubin level to below 1 mg/dl. Data from previous retrospective analyses and prospective uncontrolled studies suggest that from the inception of Omegaven® therapy, conjugated or direct bilirubin will remain elevated for approximately 8 weeks at levels comparable to those observed prior to administration of Omegaven®. Subsequently, levels are expected to fall by approximately 1 mg/dl/week until they normalize. The time to normalization will vary according to each patient's baseline conjugated or direct bilirubin level. Thus, a patient who begins Omegaven® with a conjugated or direct bilirubin level of 7 mg/dl is likely to experience normalization within 14 weeks (8+6 weeks). We will compare the group receiving Omegaven® with historical controls from our internal registry who have demonstrated cholestasis while on Intralipid®. We will compare changes in conjugated/direct bilirubin concentration over time between groups via Kaplan-Meier analysis (see Statistics section XIII).

Secondary endpoints will be: normalization of total bilirubin and liver enzymes. Differences in these values at the end of 14 weeks of therapy will be compared with those of controls via Kaplan-Meier analysis identical to that employed for conjugated and direct bilirubin levels. Furthermore, we expect that elevated triglyceride levels which might be present at the initiation of therapy will have normalized at the same time that liver profiles have normalized.

XI. Assessment of Safety/Data Safety Monitoring Board

A DSMB will monitor the study for the occurrence of adverse events (both serious and otherwise). A significant increase in the rate of adverse events would be cause for concern for the safety of participants in the study. Information on adverse events will be presented in several ways: (1) listings of serious adverse events with accompanying narrative summary by the PI; (2) summaries of adverse events by body system and type of event. This information will be presented to the DSMB.

The DSMB will also monitor the efficacy and the conduct of the study. Interim monitoring reports for the DSMB will include, but will not be limited to, such tabulations as:

1. platelet counts
2. essential fatty acid profiles
3. coagulation studies
4. liver profiles

5. renal profiles

The DSMB will meet at least once per year and possibly more frequently given the expected speed of recruitment and study medication administration.

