All adverse events will be followed until they are resolved or the patient's participation in the treatment ends (i.e., until a final report is completed for that patient).

In addition, all SAEs and those non serious events assessed by the Investigator as attributable (i.e. possibly, probably, definitely related to the drug) will continue to be followed even after the patient's participation in the treatment is over. Such events will be followed until they resolve or until the Investigator assesses them as "chronic" or "stable." Resolution of such events is to be documented in the CRF.

XIII. Statistics

We selected a study number of 25 patients (5 patients a year for 5 years) even though, statistically, a number of 19 will be satisfactory based upon power analysis. We know from our current registry that 10% of historic controls will experience resolution of cholestasis within 8 weeks while receiving Intralipid®, and we know from the data of Gura, et al (5) that approximately 50% of experimental subjects will experience resolution of cholestasis within eight weeks while receiving Omegaven®. Thus, achieving an alpha of 0.05 and a beta of 0.80, a sample size of 19 patients and 19 controls will be adequate (11). However, insofar as this is a compassionate release protocol, we will not refuse entry into the study even if we have shown statistically that Omegaven® is efficacious. We estimate that at most we will acquire five patients per year, and we anticipate that within five years, Omegaven® or SMOF (soy, MCT, olive oil and fish oil) parenteral lipids will have obtained FDA approval for clinical use.

The analysis populations will include (1) subjects receiving Omegaven® under this protocol and (2) historical controls from our internal registry who have demonstrated cholestasis while on Intralipid®. Paired t-tests will be used to report the statistical significance of differences between means. A p value of 0.05 or less will be considered significant. Wilcoxon Tests will be used to report the statistical significant differences between medians, and χ^2 tests/Fisher's exact tests will be used to report proportions. A Kaplan-Meier analysis will compare changes in conjugated/direct bilirubin concentration over time between groups. Cox proportional hazard models will be used to estimate crude and adjusted hazard ratios. Analyses will be performed via SAS 9.2 (SAS Institute Inc, Cary, NC) and S-Plus 8.1.1 (Insightful, Inc, Seattle, WA).

IX. Data Management

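### Treated children enter from 30 days after a failed soy-lipid cut, but registry controls need no such cut and have no time zero, so a late effect of lipid amount could be read as an Omegaven response

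*Combined protocol and SAP*

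**What the plan says.** - **Entry (IX.A).** Criterion 3 covers "Patients who have a conjugated or direct bilirubin of ≥ 3 mg/dl for more than 4 weeks". Criterion 4 adds that lowering soy lipid to an average below 1.2 g/kg/day "has failed to reduce the conjugated or direct bilirubin within ≥ 30 days of implementation". The 30 days is a minimum with no upper limit.
- **Effect of reduction alone (III).** "Preliminary results suggest that this strategy is beneficial for some infants, but that it is not universally effective". No response rate and no time to response are given.
- **Course expected on Omegaven (X).** After Omegaven starts, "conjugated or direct bilirubin will remain elevated for approximately 8 weeks at levels comparable to those observed prior to administration of Omegaven"; after that, "levels are expected to fall by approximately 1 mg/dl/week until they normalize". The endpoint reads: "The primary endpoint will be reduction in conjugated or direct bilirubin level to below 1 mg/dl".
- **Comparator (X and XIII).** The comparison group is "historical controls from our internal registry who have demonstrated cholestasis while on Intralipid". It is not stated that these patients had a lipid cut, that they met Criterion 4, or from which date they are followed.
- **Analysis (XIII).** Kaplan-Meier, tests of proportions, and crude and adjusted Cox hazard ratios are planned. No covariate is named. Data Collection (IX.G) does not list the date of lipid reduction.
- **Sample size (XIII).** Resolution within eight weeks is taken as 10% on Intralipid and about 50% on Omegaven, giving 19 patients and 19 controls. Enrolment is set at 25.

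**The concern.** Section II asks whether replacing one type of lipid with another reverses cholestasis. Every treated child has, by Criterion 4, recently had a change in lipid amount. Section X expects bilirubin to stay flat for about 8 weeks after the switch to Omegaven, yet Criterion 4 can judge the earlier change at 30 days. The protocol does not explain the two horizons.

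Some children may respond to the cut later than the day they enter. They satisfy Criterion 4 correctly, because their bilirubin is flat at Day 0, and then recover during the Omegaven observation period. If the controls had no cut, or were further past one, they have no matching recovery and the comparison tilts towards Omegaven. With no concurrent control group, nothing else in the plan separates lipid amount from lipid type.

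**Working it through.** **Inputs.** From the documents: minimum wait w = 30 days (IX.A); lag 56 days and fall 1 mg/dl per week, both stated for Omegaven only (X); endpoint below 1 mg/dl (X); entry bilirubin B of at least 3 mg/dl (IX.A); 10%, 50%, 19+19 and 25 patients (XIII). Not in the documents, so assumed: the lag L after a soy-lipid cut, and the treated resolution rate q if Omegaven does nothing.

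**1. The plan's own figure.** I read the stated beta of 0.80 as power. For 10% v 50%, two-sided 0.05, pooled normal approximation without continuity correction:
n = [1.96·√(2·0.3·0.7) + 0.842·√(0.1·0.9 + 0.5·0.5)]² / 0.4² = 19.4, so 20 per group. At 19 per group power is 79.2%. The stated 19 is reproduced to within rounding and choice of formula. It takes the registry's 10% as the rate the treated children would have had without Omegaven.

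**2. When a late effect would appear.** It begins (L − w) days after Day 0 if L exceeds w. If L ≤ 30, responders are already falling by day 30 and Criterion 4 removes them. If L = 56 and w = 30, it begins 26 days (3.7 weeks) after Day 0. If L = 56 and the child is still flat beyond day 56, there is no late effect left to appear.

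**3. Time to the endpoint if L and the slope equalled Section X's Omegaven figures (assumption), w = 30.** Weeks to 1 mg/dl = 3.7 + (B − 1), against Section X's 8 + (B − 1) on Omegaven:

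| B (mg/dl) | Late effect of the cut | Section X, Omegaven |
|---|---|---|
| 3 | 5.7 | 10 |
| 5 | 7.7 | 12 |
| 7 | 9.7 | 14 |

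Under this assumption, baselines up to 1 + (8 − 3.7) = 5.3 mg/dl would resolve inside the eight-week window of the sample-size calculation.

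**4. The other timing figure.** To resolve by week 8 at 1 mg/dl per week, a child must start falling by day 56 − 7(B − 1): day 42 for B = 3, day 28 for B = 5, day 14 for B = 7. The implied lag is below 30 days for any B above 1 + 26/7 = 4.7 mg/dl. Section X, by contrast, puts the earliest resolution at week 10 (B = 3), so its plateau and XIII's 50% within eight weeks cannot both hold. If a soy-lipid cut shared the lag implied by XIII, the gap would be at most 42 − 30 = 12 days (at B = 3) and nil above 4.7 mg/dl.

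**5. Illustration of size.** Omegaven inert, controls at 10%, treated at q; exact probability of two-sided p ≤ 0.05 in favour of Omegaven. The 25 controls in the second pair of columns are my assumption.

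| q | Fisher 19+19 | χ² 19+19 | Fisher 25+25 | χ² 25+25 |
|---|---|---|---|---|
| 10% | 0.5% | 1.8% | 0.4% | 2.4% |
| 20% | 6.6% | 12.8% | 8.5% | 17.2% |
| 25% | 13.2% | 22.2% | 18.0% | 30.0% |

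These use proportions, as the sample size does. They show what a given excess would do, not how large the excess is.

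**The case against.** The strongest objection is that the 8-week lag belongs to Omegaven. Carrying it over to soy-lipid reduction is an analogy. Sections I and III give both strategies a common rationale, less phytosterol exposure, but no timing for reduction. Section XIII's eight-week resolution rate also points to a shorter lag. This stands: the bias is conditional.

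Three stronger readings are tempting, and the documents do not support them.
- *Criterion 4 screens out no late responders.* The 30 days is a floor. Under an 8-week lag, anyone who waited longer and responded would already have been excluded. The distribution of waits is unknown.
- *Late responders do enter and are credited to Omegaven.* That is a risk of unknown size, not a stated fact.
- *Section III's one quarter can be added to the 10%.* That quarter is total reversal on soy lipid, conditional on intestinal adaptation and mostly enteral calories, with no time window. Adding it to the 10% would put recovery on soy lipid at 35%, above the quarter itself. I therefore cap q at 25%, and even that is only illustrative.

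It can also be said that adjusted Cox models are planned, and that controls with the same history and index date would carry the same late responders. Both are true. But no covariate is named, and nothing requires controls of that kind. That gap does not depend on any assumption about lag.

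**Conclusion.** The point holds in a conditional form. What the documents establish is an asymmetry: treated children enter after a recent failed lipid cut, while controls need no cut and have no time zero, and no covariate is named to bridge the two. As written, a late effect of lipid amount cannot be separated from an effect of lipid type.

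Whether this biases the result depends on three unknowns: the lag after a soy-lipid cut, how long children wait before Day 0, and the lipid history of the controls. The bias is nil if the lag is 30 days or less. If late responders raised the treated rate from 10% to between 20% and 25%, an inert Omegaven would be declared better by Fisher's test in 7% to 13% of trials at 19+19 and 9% to 18% at 25+25, against about 0.5% with equal rates. Sections X and XIII must be reconciled on time to response before either is used to argue the lag.

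**What to change.** Leave eligibility and treatment as they are.

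1. **X and XIII, controls.** Select registry controls who also met the lipid-reduction condition of Criterion 4. Set their time zero at the date they met it, or at a time since reduction matched to the treated children. Matching is safer if many treated children start well after day 30, since otherwise the two clocks start at different distances from the cut.
2. **IX.G, data.** Record the date of soy-lipid reduction in both groups. For treated children it is already needed to judge Criterion 4.
3. **XIII, model.** Name time from reduction to time zero, kept continuous, as a covariate in the adjusted Cox model. On the plan's own rates, 25+25 yields about 12.5 + 2.5 = 15 resolutions, too few to support splitting this variable into strata.
4. **XIII, sensitivity.** Prespecify an analysis limited to children with a longer period on reduced lipid, for example 8 weeks or more, and state that this cut-off is an assumption.
5. **X, interpretation.** State that recovery soon after a recent lipid cut cannot be attributed to lipid type alone. Reconcile the 8-week plateau with XIII's eight-week resolution rate.

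The cost is one extra date per child, fewer eligible controls, and a small, imprecise sensitivity subset. The 10% should be re-derived in the selected controls. If it were 15%, 20% or 25% against 50%, power at 19+19 would be 64%, 49% or 35%.
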